#### ***10.1.2 Interim Analyses***

No interim analyses are planned.

#### ***10.1.3 Missing, Unused, and Spurious Data***

Patients with missing efficacy data or indeterminate outcomes will be considered as treatment failures for efficacy analyses.

For the primary endpoint, patients who discontinued for lack of efficacy or rescue medication use will be considered as treatment failure.

If the “ear pain” continues at the end of the study, the TEOP will be recorded as the length of time between the time of the first dose of study medication and the last time point when a pain measurement was recorded.

Patients who take rescue medication, discontinue or are lost to follow up, and for whom the pain persists at the time of the last observation, will be censored at maximum length (Day 17) in those cases when the diary information is not available.

To explore the effect of the handling of the missing data and assess the robustness of the efficacy results, a complete case analysis will be carried out (i.e. all efficacy analyses will be repeated on actual values i.e. without imputation of the missing data) as sensitivity analysis.

All data, whether summarized or not, will be presented in the data listings.

Spurious data, such as unscheduled visit collections, laboratory tests not specified in the protocol, or Investigator comments, will be presented in the data listings. These data will be excluded from the summary tables.

#### ***10.1.4 Analysis Populations***

There will be 5 populations defined for this study: Safety, Clinical intent-to-treat (CITT), Microbiological intent-to-treat (MITT), Clinical per-protocol (CPP), and Microbiological per-protocol (MPP).

The **Safety population** will include all patients who received any study medication.

The **CITT population** will include all patients who were randomized.

The **MITT population** will include all CITT patients whose Visit 1 microbiological culture yields 1 or more pathogens, as defined in Section 7.1.2.

The **MITT-PA/SA population** will include the pathogen positive subset of the CITT population which includes all patients who received study medication and had culture positive for *P. aeruginosa* and/or *S. aureus* at baseline in the evaluable ear.

The **CPP population** will include all CITT patients who:

- Satisfied all inclusion and exclusion criteria;
- Did not receive any prohibited concomitant medications;
- Did not have any other major protocol violations;

- Completed Visit 3 and Visit 4 (unless the patient was deemed a clinical failure at an earlier visit than Visit 4); and
- Had compliance rates between 80% and 120% as defined in Section 10.1.8 (patients who are deemed Clinical Failures are to be included if they had compliance rates between 80% and 120% during the first 3 days of study treatment).

The **MPP population** will include all CPP patients whose Visit 1 microbiological culture yields 1 or more pathogens and who had microbiological results (when patient has material to culture) from Visit 3 and/or Visit 4 unless the patient was deemed a clinical failure at an earlier visit than Visit 4.

For the CITT and MITT populations, the treatment group of a patient will be determined by the treatment group to which the patient was randomized.

For the Safety, CPP and MPP populations, the treatment group of a patient will be determined by the treatment the patient received, not necessarily the group to which he or she was randomized. The Safety population will be used for all safety analyses.

The primary populations for efficacy analyses will be the MITT population.

The populations to be used for each of the secondary efficacy endpoints will be detailed in the Statistical Analysis Plan.

#### **10.1.5 Patient Disposition**

The numbers of patients in each treatment group who completed the study and who terminated early will be tabulated. For patients who terminated early, primary and secondary reasons for termination will be tabulated. Patients who were excluded from each of the study populations defined in Section 10.1.4, and their reasons for exclusion, will be listed.

#### **10.1.6 Demographics and Baseline Characteristics**

Continuous demographic and baseline characteristics, such as age, will be summarized by treatment group with descriptive statistics (n, mean, standard deviation, standard error of the mean, median, minimum, and maximum). Categorical demographic and baseline characteristics such as gender and race will be tabulated (frequency and percent) by treatment group and category. Demographic and baseline characteristic tables will be presented for all study populations.

#### **10.1.7 Protocol Deviations**

Protocol deviations are defined as violations from the procedures outlined in the protocol. **Major** protocol deviations are protocol violations likely to affect the study results and leading to the exclusion of the patient from the CPP.

Once the database has been completed and considered as “clean”, a data blind review will be conducted before the database lock in order to identify all major protocol violations and assign patients into each of the analysis sets as defined in section 10.1.4.

Patients with protocol deviations will be presented in the data listings. Protocol violations will be tabulated by treatment group and violation.

#### ***10.1.8 Compliance with Study Medication***

Compliance will be assessed by a review of the patient diary. The number of doses the patient actually took during a given period will be divided by the number of doses the patient was expected to take during that period. The resulting ratio will be multiplied by 100% to determine percent compliance. Percent compliance during the treatment period and during the first 3 days of the treatment period will be calculated and listed for each patient.

The percent compliance during the first 3 days is needed to identify the clinical failures whom will remain in the CPP population, as mentioned in Section 10.1.4.

Patients will be considered “compliant” if their percent compliance is between 80% and 120%. The proportion of patients who were compliant and non-compliant during the treatment period will be tabulated by treatment group.

#### ***10.1.9 Concomitant Medications***

Concomitant medications will be tabulated by treatment group and by type of pain treatment. If the concomitant medications analysis by type of pain treatment shows difference between treatment groups, subgroup analyses by type of pain treatment might be carried out on efficacy results as post-hoc analyses.

#### ***10.1.10 Efficacy Analyses***

Only assessments from the evaluable ear will be used for the efficacy analyses.

##### ***10.1.10.1 Primary efficacy endpoint***

###### ***Primary analysis of the primary endpoint***

The primary efficacy endpoint will be the therapeutic cure at Visit 3 in the MITT-PA/SA population.

In order for the requirements of the combination policy to be satisfied, both comparisons of the combination to the components alone must show the combination to be statistically significantly better than the component alone using a two-sided 0.05 significance level.

The number and percentage of patients with therapeutic cure at Visit 3 will be summarized by treatment group. The proportion of patients with a therapeutic cure will be compared between the treatment groups by using a chi-squared test.

Efficacy analyses of the primary endpoint will also be conducted on the MITT, MPP, CITT and CPP populations.

##### ***10.1.10.2 Secondary efficacy endpoints***

Only analysis of the principal secondary endpoint will be confirmatory. Analysis of the other secondary efficacy endpoints will be supportive only. Since each confirmatory comparison (Ciprofloxacin 0.3% plus Fluocinolone acetonide 0.025% otic solution over Ciprofloxacin 0.3% otic solution alone and over Fluocinolone acetonide 0.025% otic solution alone for the primary endpoint, and for the principal secondary endpoint) should be

statistically significant at a two-sided 0.05 significance level, no adjustment for multiple comparisons/multiplicity will be made.

### **Principal secondary endpoint**

#### Time to end of ear pain

Patients or caregivers will complete a diary twice daily (prior to dosing) in which they will record assessments of ear pain and pain medication use, including the time and date of the assessment.

Ear pain is defined as ending on the first day (morning or evening) on which there is no use of analgesics, the diary pain score is zero and the score remains at zero for all subsequent visits until the end of the study.

The patient diary information together with investigator assessment will be used to ascertain the time point (morning or evening) and date at which the ear pain in the evaluable ended without use of analgesics. The time to end of ear pain is the interval (in days) between the first dose of study medication and the time when the ear pain in the evaluable ended without use of analgesics.

If ear pain in the evaluable ear continued to the end of the study, the TEOP will be recorded as the length of time between the time of the first dose of study medication and the last time point when a pain measurement was recorded.

Patients who took rescue medication, discontinued or were lost to follow up, and for whom the pain persisted at the time of the last observation, will be censored at maximum length (Day 17) in those cases when the diary information is not available.

The null hypothesis is that there is no difference in time to end of pain between the combination and the components alone. The alternative hypothesis is that there is a difference in time to end of pain between the combination and the components alone. The comparison of the treatment groups will be made by using the log-rank test stratified on age (6 months to younger than 18 years old versus 18 years and older), and a difference will be claimed if the null hypothesis can be rejected at the two-sided 0.05 level.

### **Other secondary endpoints**

#### Sustained Microbiological cure

For any patient with a culture positive for a pathogen at Visit 1, bacteriological response at Visits 3 will be classified as Eradication, Presumed Eradication, Persistence, Presumed Persistence, Superinfection or Indeterminate and bacteriological response at Visit 4 will be classified as Eradication, Presumed Eradication, Persistence, Presumed Persistence, Recurrence, Superinfection, Reinfection or Indeterminate (as defined in Section 7.1.2).

The number and percentage of patients with each response will be summarized by visit and treatment group. The proportion of patients with sustained microbiological cure i.e. with a response of Eradication or Presumed Eradication at both Visit 3 and Visit 4 will be compared between the Ciprofloxacin containing products (Ciprofloxacin 0.3% plus

Fluocinolone acetonide 0.025% otic solution and Ciprofloxacin 0.3%) and the Fluocinolone acetonide 0.025% otic solution treatment groups by using chi-squared test.

#### Overall clinical outcome at Visit 3 and Visit 4

The Investigator will make the assessment of Clinical Outcome for each patient at Visit 3 and at Visit 4. Clinical Outcome will be classed as Clinical cure or Clinical failure (as defined in Section 7.1.1.5).

The number and percentage of patients with each outcome will be summarized by visit and treatment group. For each visit, the proportion of patients with a response of Clinical success will be compared between the treatment groups by using a chi-squared test.

Overall clinical outcome will also be summarized by bacterial species identified as “target OTIC organism” (*P. aeruginosa* and *S. aureus*).

#### Microbiological outcome at Visit 3 and Visit 4

The proportion of patients with a response of Eradication or Presumed Eradication at Visit 3 and Visit 4 will be compared between the Ciprofloxacin 0.3% plus Fluocinolone acetonide 0.025% otic solution and the Fluocinolone acetonide 0.025% otic solution and between Ciprofloxacin 0.3% otic solution and Fluocinolone acetonide 0.025% otic solution treatment groups by using a chi-squared test.

#### Therapeutic cure at Visit 4

The number and percentage of patients with therapeutic cure at Visit 4 will be summarized by treatment group. The proportion of patients with a therapeutic cure will be compared between the treatment groups by using a chi-squared test.

#### Change in Brighton grading at Visit 3 and Visit 4

Brighton grading will be assessed by the Investigator at Visits 1, 3 and 4, as defined in Section 7.1.1.1.

The number and percentage of patients with each grade will be summarized by visit and treatment group.

For the 3-level response, the proportion of patients with a Brighton grading of “0” will be considered as Resolved. It will be considered as “Improved” at Visit 3 and Visit 4 if the grade is lower than the previous visit. Brighton grading will be considered as “Not Improved” otherwise. Furthermore if Brighton grading is considered “Not Improved” or “Improved” in the 3-level response then it will be identified as “Not Resolved” in the 2-level response. If it is considered “Resolved” in the 3-level response then it will also be considered “Resolved” in the 2-level response.

For Visits 3 and 4, the proportion of patients with a response of Resolved and Not Resolved will be compared between the treatment groups by using a Chi-square test.

#### Change in otorrhea at Visit 3 and Visit 4

Otorrhea will be assessed by the Investigator at Visits 1, 3 and 4. Otorrhea will be assessed as Severe, Moderate, Mild or Absent (as defined in Section 7.1.1.4). Otorrhea will be considered resolved at Visits 3 and 4 if the eardrum edema is assessed as Absent.

The number and percentage of patients with each outcome (Severe, Moderate, Mild or Absent) will be summarized by visit and treatment group. For Visits 3 and 4, the proportion of patients with a response of Resolved and Not Resolved will be compared between the treatment groups by using a Chi-square test.

For the 3-level response, otorrhea will be considered as “Improved” at Visit 3 and Visit 4 if otorrhea is assessed by the investigator as “Mild” and was assessed as “Severe” or “Moderate” at Visit 1 (Day 1) or if otorrhea was assessed by the investigator as “Moderate” at Visit 3 or Visit 4 and was assessed as “Severe” at Visit 1. Otorrhea will be considered as “Not Improved” otherwise. Furthermore if otorrhea is considered “Not Improved” or “Improved” in the 3-level response then it will be identified as “Not Resolved” in the 2-level response. If otorrhea is considered “Resolved” in the 3-level response then it will also be considered “Resolved” in the 2-level response.

#### Changes in edema at Visit 3 and Visit 4

Edema will be assessed by the Investigator at Visits 1, 3 and 4. Edema will be assessed as Severe, Moderate, Mild or Absent (as defined in Section 7.1.1.3). Edema will be considered resolved at Visits 3 and 4 if the eardrum edema is assessed as Absent. Edema will be considered improved at Visits 3 and 4 if the edema is assessed as Mild.

The number and percentage of patients with each outcome (Severe, Moderate, Mild or Absent) will be summarized by visit and treatment group. In addition, the number and percentage of patients with eardrum edema considered resolved, improved or not improved will be summarized at Visits 3 and 4 by treatment group. For Visits 3 and 4, the proportion of patients with a response of Resolved and Not Resolved will be compared between the treatment groups by using a Chi-square test.

For the 3-level response, edema will be considered as “Improved” at Visit 3 and Visit 4 if the edema is assessed by the investigator as “Moderate” and was assessed as “Severe” at Visit 1. Edema will be considered as “Not Improved” otherwise.

Furthermore if edema is considered “Not Improved” or “Improved” in the 3-level response then it will be identified as “Not Resolved” in the 2-level response. If edema is considered “Resolved” in the 3-level response then it will also be considered “Resolved” in the 2-level response.

#### Changes in pain at Visit 3 and Visit 4

Pain will be assessed at Visits 1, 2, 3 and 4. Pain will be assessed as Severe, Moderate, Mild, Absent or Unable to assess (as defined in Section 7.1.1.2). Pain will be considered resolved at 3 and 4 if the pain is assessed as Absent. Pain will be considered improved at Visits 3 and 4 if the pain is assessed as Mild.

The number and percentage of patients with each outcome (Severe, Moderate, Mild or Absent) will be summarized by visit and treatment group. In addition, the number and percentage of patients with pain considered resolved, improved or not improved will be summarized at Visits 2, 3 and 4 by treatment group. For Visits 2, 3 and 4, the proportion of patients with a response of Resolved will be compared between the treatment groups by using a chi-squared test.

For the 3-level response, pain will be considered as “Improved” at Visit 3 and Visit 4 if the pain is assessed by the investigator as “Moderate” and was assessed as “Severe” at Visit 1. Pain will be considered as “Not Improved” otherwise.

Furthermore if pain is considered “Not Improved” or “Improved” in the 3-level response then it will be identified as “Not Resolved” in the 2-level response. If pain is considered “Resolved” in the 3-level response then it will also be considered “Resolved” in the 2-level response.

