#### 7.1.1.4 *Otorrhea*

Otorrhea in both ears will be assessed at Visits 1, 3, and 4 by the investigator. For consistency, the same individual should do the assessments at all 3 visits if possible. Otorrhea will be assessed as:

- Severe (3),
- Moderate (2),
- Mild (1),
- Absent (0).

At Visits 3 and 4, otorrhea will be considered resolved if the otorrhea level is 0. Otorrhea will be considered improved if the otorrhea level is lower than in the previous visit.

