If a patient took rescue medication prior to Visit 3, the response will be considered not resolved at Visit 3. Similarly, if a patient took rescue medication prior to Visit 4, the response will be considered not resolved at Visit 4.

For Visits 3 and 4, the proportion of patients with a response of Resolved and Not Resolved will be compared between the treatment groups by using the same Chi-squared test as the primary efficacy endpoint.

A by-patient listing of edema data will be provided.

Otorrhea

Otorrhea will be assessed by the Investigator at Visits 1, 3 and 4. Otorrhea will be assessed as Severe, Moderate, Mild, or Absent as defined in Section 4.7.2.

The number and percentage of patients with each outcome (Severe, Moderate, Mild or Absent) will be summarized by visit and treatment group.

Assessments will also be summarized in terms of a 3-level and a 2-level response. For the 3-level response, otorrhea will be considered resolved at Visits 3 and 4 if the otorrhea is assessed as Absent. Otorrhea will be considered as "Improved" at Visit 3 and Visit 4 if otorrhea is assessed by the investigator as "Mild" and was assessed as "Severe" or "Moderate" at Visit 1 (Day 1) or if otorrhea was assessed by the investigator as "Moderate" at Visit 3 or Visit 4 and was assessed as "Severe" at Visit 1. Otorrhea will be considered as "Not Improved" otherwise. Furthermore if otorrhea is considered "Not Improved" or "Improved" in the 3-level response then it will be identified as "Not Resolved" in the 2-level response. If otorrhea is considered "Resolved" in the 3-level response then it will also be considered "Resolved" in the 2-level response.

If a patient took rescue medication prior to Visit 3, the response will be considered not resolved at Visit 3. Similarly, if a patient took rescue medication prior to Visit 4, the response will be considered not resolved at Visit 4.

For Visits 3 and 4, the proportion of patients with a response of Resolved and Not Resolved will be compared between the treatment groups by using the same Chi-squared test as the primary efficacy endpoint.

A by-patient listing of otorrhea data will be provided.

Ear Pain Scales

Ear pain scales will be assessed by the patient twice a day in the patient's Diary Card to calculate the TEOP. The ear pain scales assessed at Visit 3 and Visit 4 will be categorized as follows:

- Disappeared if there is no ear pain
- Improved if the response is better than the response at Visit 1

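### Protocol 10.1.10.2 scores otorrhea as resolved when edema is absent, against Protocol 7.1.1.4 and the SAP; two lesser inconsistencies in its edema and pain rules also need correcting

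*Protocol*

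**What the plan says.** **Otorrhea.** Protocol 10.1.10.2 says "Otorrhea will be considered resolved at Visits 3 and 4 if the eardrum edema is assessed as Absent", then plans a chi-squared comparison of Resolved against Not Resolved at Visits 3 and 4. Protocol 7.1.1.4 says "At Visits 3 and 4, otorrhea will be considered resolved if the otorrhea level is 0". SAP 4.7.3 says "otorrhea will be considered resolved at Visits 3 and 4 if the otorrhea is assessed as Absent".

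**Edema and pain.** For edema, Protocol 10.1.10.2 first says "Edema will be considered improved at Visits 3 and 4 if the edema is assessed as Mild". Its 3-level rule then gives Improved only "if the edema is assessed by the investigator as “Moderate” and was assessed as “Severe” at Visit 1", with every other unresolved result Not Improved. Pain follows the same pattern: "Pain will be considered improved at Visits 3 and 4 if the pain is assessed as Mild", and then a 3-level rule that names only Severe to Moderate. Protocol 7.1.1.2 and 7.1.1.3 define improvement as a level below that of the previous visit. SAP 4.7.3 measures it from Visit 1 and counts both Mild from Moderate or Severe, and Moderate from Severe.

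**Pain at Visit 2.** Protocol 10.1.10.2 says "For Visits 2, 3 and 4, the proportion of patients with a response of Resolved will be compared between the treatment groups". Protocol 7.1.1.2 and Table 1 grade otalgia at Visits 1, 3 and 4 only, and Visit 2 is a telephone call. SAP 4.7.3 grades otalgia at Visits 1, 3 and 4 and tests it at Visits 3 and 4.

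**The concern.** Protocol 10.1.10.2 is the operative analysis section. Its otorrhea sentence ties a tested endpoint to a different sign, so a programmer who followed it would report the edema result twice, once under the otorrhea label. The edema and pain paragraphs give a fall to Mild two labels. The pain paragraph schedules a comparison for which the protocol plans no data.

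The SAP uses other rules on each point and does not say that it departs from the protocol. Neither document states which prevails. SAP section 1 describes the SAP as adding detail to the protocol, Protocol 11.4 asks for the protocol to be followed exactly, and SAP 4.11 is general and lists none of these differences. At stake is the consistency of supportive results and the traceability of their definitions.

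**Working it through.** The plan states no figure for this point. The check applies each rule to every possible grade combination (0 Absent, 1 Mild, 2 Moderate, 3 Severe).

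**1. Otorrhea by edema.** There are 4 × 4 = 16 combinations.

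- The literal rule in 10.1.10.2 (edema = 0) scores 4 combinations Resolved. In 3 of them discharge is still present (otorrhea 1, 2 or 3 with edema 0).
- The rule in 7.1.1.4 and the SAP (otorrhea = 0) also scores 4 combinations Resolved. In 3 of them edema is present (otorrhea 0 with edema 1, 2 or 3), and the literal rule calls these Not Resolved.
- The rules therefore disagree in 3 + 3 = 6 of 16 combinations and agree in 10. Under the SAP rule none is misclassified.
- The edema paragraph uses the same criterion for edema, so the literal otorrhea test and the edema test classify every patient identically.
- The sentence also conflicts with the 3-level otorrhea rule in the same subsection, which uses otorrhea grades. Discharge falling from Moderate to Mild with edema absent would be both Resolved and Improved.

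**2. Edema and pain.** Protocol 5.1 requires grade 2 or more for both at entry. I assume the evaluable ear meets this.

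| Visit 1 → later | 10.1.10.2, first sentence | 10.1.10.2, 3-level rule read literally | SAP 4.7.3 | 7.1.1 at Visit 3 |
|---|---|---|---|---|
| Moderate → Mild | Improved | Not Improved | Improved | Improved |
| Severe → Mild | Improved | Not Improved | Improved | Improved |
| Severe → Moderate | not covered | Improved | Improved | Improved |
| Moderate → Moderate or Severe | not covered | Not Improved | Not Improved | Not Improved |
| Severe → Severe | not covered | Not Improved | Not Improved | Not Improved |
| either → Absent | Resolved | Resolved | Resolved | Resolved |

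Read literally, the 3-level rule places Severe to Mild below Severe to Moderate. The planned tests at Visits 3 and 4 do not change, because Improved and Not Improved both become Not Resolved in the 2-level response.

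**3. Reference visit.** At Visit 3 the previous graded visit is Visit 1, so the SAP and 7.1.1 agree. At Visit 4 there are 2 baseline grades × 4 Visit 3 grades × 4 Visit 4 grades = 32 combinations. The two rules disagree in 8: in 7 only the SAP gives Improved, and in 1 (Moderate, Severe, Moderate) only 7.1.1 does. Correcting 10.1.10.2 alone therefore leaves open which rule governs the tables.

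**4. Pain at Visit 2.** Protocol 7.1.1.2 and Table 1 plan no grade at this visit. The pain paragraph defines resolution only for Visits 3 and 4. Protocol 8.2.2 has staff ask whether symptoms are improving or worsening, which does not give a 0–3 grade. As written, the comparison has neither a planned input nor a definition of response.

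**5. Reach.** Protocol 10.1.10.2 calls these endpoints supportive. Therapeutic cure uses a total score of 0 built from the otorrhea grade itself (Protocol 7.1.1.5 and 7.1.3, SAP 4.7.2). Time to end of pain comes from diary pain scores and analgesic use. None of the three rules enters either endpoint.

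**The case against.** The strongest answer is that the SAP is right on all three points, and that Protocol 10.2 treats the SAP as the reference for reporting deviations. A team programming from the SAP would make none of these errors. The otorrhea sentence is plainly a copying slip: the same paragraph refers to 7.1.1.4 for the grades, and the wording matches the edema sentence. All of this stands and keeps the practical risk low. It does not remove the need for a correction, since the protocol text is current, defines a tested endpoint by the wrong sign, and is overridden by no precedence statement.

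Four stronger readings are tempting, and the documents do not support them.

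- *The trial will report wrong results.* That follows only if the analysis uses the protocol sentence in place of the SAP rule.
- *The edema and pain response tables are certainly inverted.* The two sentences can be read as additive, so that Mild counts as improved and so does Severe to Moderate. With entry grades of 2 or more, that union equals the SAP rule. The text is ambiguous, and only descriptive tables are involved.
- *The Visit 2 comparison gives a false result, or is proven impossible.* It lacks planned grades and a definition of resolved. The telephone questionnaire is not in the documents, so its content cannot be checked.
- *The primary endpoint is affected because the objective speaks of otorrhea being resolved.* Protocol 7.1.3 and SAP 4.7.2 make cure operational through a total score of 0.

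**Conclusion.** The point holds as a correction to the protocol. One sentence would, if followed, turn the otorrhea resolution test at Visits 3 and 4 into a copy of the edema test, with 6 of 16 grade combinations misclassified. This is a count of combinations, not a share of patients. The documents give no rate at which edema and discharge disagree, so the number of patients cannot be estimated.

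The Mild conflict is a drafting ambiguity confined to the 3-level tables. The Visit 2 pain comparison is a planned analysis without planned data. Importance is low: the endpoints are supportive, the SAP already has workable rules, and neither confirmatory endpoint changes. The edema and pain result assumes that the evaluable ear meets the entry grades; the otorrhea result needs no assumption beyond the four-point scales.

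**What to change.** Correct Protocol 10.1.10.2 to the SAP 4.7.3 rules:

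- Otorrhea is resolved when otorrhea is Absent.
- Edema and pain are Improved when Mild after Moderate or Severe at Visit 1, or Moderate after Severe at Visit 1. Delete the separate sentences that define improved as Mild.
- Pain is compared at Visits 3 and 4 only; remove Visit 2 from the assessment, summary and test sentences.

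Add a statement to SAP 4.11 that these rules replace the protocol's for the 3-level sign and symptom tables. Leave the previous-visit rule for Clinical Improvement on the total score in Protocol 7.1.1.5 unchanged, and do not rewrite improved in 7.1.1.2 to 7.1.1.4. Section 7.1.1.5 cites those sections, and Clinical Improvement feeds the Presumed Eradication category in 7.1.2.

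The cost is a wording correction to the protocol and a short SAP revision before database lock. It needs no new data and no change to analyses programmed from SAP 4.7.3.
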